11.0 Regulatory Requirements

11.1 Informed Consent

During the SCREENING PROCESS, the screening website and the research staff (or PI) will obtain digital or verbal consent from each participant (see online screener and phone screener, attached). Potential participants will be contacted by phone to assess their interest in participating; although we will note in the phone script that we are affiliated with UIC, we will also explain that they are under no obligation to participate and that their decision to participate has no influence on their clinical care at UIC (if applicable).

In addition, at the ENROLLMENT VISIT, trained members of the research team will obtain full written or digitally-signed informed consent from the participant using the following documented process:

Interested participants will visit the laboratory in-person or have virtual online sessions for their enrollment session where they will each read the consent form.

Research personnel will then ask if the participant has any questions they would like answered.

The participant will sign the consent form, witnessed by research personnel. The original consent form will be maintained in the participant's file, along with documentation that the participant's questions were answered by the informational sheet or that research personnel gave them an opportunity to ask questions. These documents will be secured in [name] locked laboratory. A copy of the consent form will be provided to the participant. For participants who completed virtual enrollment visits during the covid-19 pandemic, their consent will first be obtained through a secure online survey and then be re-assessed during their welcome visit, where they will provide written consent and given a copy of the consent form.

11.2 Subject Confidentiality

Participant confidentiality is strictly held in trust by the participating investigators, their staff, and the sponsor(s) and their agents. This confidentiality is extended to cover testing of biological samples in addition to the clinical information relating to participants. Therefore, the study protocol, documentation, data, and all other information generated will be held in strict confidence. No information concerning the study or the data will be released to any unauthorized third party.

Study participant research data, which is for purposes of statistical analysis and scientific reporting, will be transmitted to and stored on protected servers at UIC. Identifying information will be linked to ID number only in one separate password-protected file on the UIC server. These ID numbers will not contain any identifying information (e.g., initials,

birthdates, SSN) and the file linking the study ID number to identifying information will be kept in a password-protected file, separate from any study data on a UIC Psychiatry password protected drive. De-identified, coded data may be transmitted by hand or scanned and transmitted via email among the research team.

Post-Study Disposition of identifiable data or human biological materials. Once data collection is completed and data are cleaned for analysis (within 1 year after the completion of data collection), data will be de-identified and the dataset including any identifiers will be destroyed. Recordings of study interviews will be deleted immediately following weekly review by the PI. Biological samples will be destroyed according to OSHA procedures once assay is completed.

Certificate of Confidentiality

To further protect the privacy of study participants, a Certificate of Confidentiality will be obtained from the NIH. This certificate protects identifiable research information from forced disclosure. It allows the investigator and others who have access to research records to refuse to disclose identifying information on research participation in any civil, criminal, administrative, legislative, or other proceeding, whether at the federal, state, or local level. By protecting researchers and institutions from being compelled to disclose information that would identify research participants, Certificates of Confidentiality help achieve the research objectives and promote participation in studies by helping assure confidentiality and privacy to participants.

11.3 Unanticipated Problems

Definition of Unanticipated Problems (UPs)

For the purposes of this study, we will consider unanticipated problems involving risks to participants or others to include, in general, any incident, experience, or outcome that meets all of the following criteria:

- Unexpected in terms of nature, severity, or frequency given (a) the research procedures that are described in the protocol-related documents, such as the IRB-approved research protocol and informed consent document; and (b) the characteristics of the participant population being studied;
- Related or possibly related to participation in the research (“possibly related” means there is a reasonable possibility that the incident, experience, or outcome may have been caused by the procedures involved in the research); and
- Suggests that the research places participants or others at a greater risk of harm (including physical, psychological, economic, or social harm) than was previously known or recognized.

Reporting of Unanticipated Problems

Incidents or events that meet criteria for UPs require the creation and completion of an UP report form. The PI will report UPs to the IRB and to the study sponsor. The UP report will include the following information:

- Protocol identifying information: protocol title and number, PI’s name, and the IRB project number;
- A detailed description of the event, incident, experience, or outcome;
- An explanation of the basis for determining that the event, incident, experience, or outcome represents an UP;
- A description of any changes to the protocol or other corrective actions that have been taken or are proposed in response to the UP.

To satisfy the requirement for prompt reporting, UPs will be reported using the following timeline:

- All UPs will be reported to the IRB, the DSMB, and to the study sponsor within 1 week of the investigator becoming aware of the event.

Statistical Analysis Plan

Project Title: Cyclical Neuroactive Steroid Changes, Arousal, and Proximal Suicide Risk: An Experimental Approach

Principal Investigator: [name]

Approved as of September 24, 2019

Statistical Analysis Plan

There are twelve total outcomes, which are specified and numbered (#) below. In order to better set up the power analysis details that follow, I have noted the anticipated intra-class correlations for each outcome (in red) and note from which preliminary data these estimates arise.

OUTCOME SPECIFICATION

- Suicide Outcome Variables. In our primary analyses, proximal suicide risk will be operationalized as (1) daily severity of suicidal ideation using the total score on the Adult Suicidal Ideation Questionnaire in the daily survey (ICC=.64 in K99 trial), (2) daily suicidal planning thoughts (dichotomous) on the daily C-SSRS phone risk screen (~10% of days were positive for planning in the K99 trial; ICC=.45 in K99 trial) and (3) daily suicide attempt (dichotomous; aborted, interrupted, or full) on the daily C-SSRS phone risk screen (~1.2% of days were positive for suicide attempt in the K99 trial; ICC=.12 in K99 trial).
- Aim 1 Mediation Outcomes (for Mediation by Hopelessness, Arousal). Aim 1 focuses on mediation of our experimental effects by hopelessness, hyperarousal, and their interaction. The primary hopelessness outcome will be (4) daily hopelessness on items from the Beck Hopelessness Scale (validated against full BHS in the laboratory; ICC=.32 in K99 trial). The primary arousal outcomes will be (5) daily hyperarousal as measured with the Brief Agitation Measure (validated against POMS Arousal subscale in the laboratory; ICC=.26 in K99 trial), (6) daily total smartphone accelerometer displacement reflecting overall locomotor activity (measured continuously using our BiAffect app, per reviewer recommendation; ICC=.54 in Co-I [name]'s prior study in patients with bipolar disorder), and (7) daily average typing speed instability reflecting greater reactivity to external stimuli (measured using our Biaffect App; ICC=.38 in Co-I [name]'s prior study in patients with bipolar disorder), (8) degree of RSA withdrawal during the Face Matching Task (no ICC estimate available for repeated administration; we assume a moderate ICC between .4-.6), and (9) degree of PEP shortening during the Face Matching Task (no ICC estimate available for repeated administration; we assume a moderate ICC between .4-.6).
- Aim 2 Mediation Variables (Mediation by Neurosteroids and Neurosteroidogenic Enzymes). Aim 2 focuses on mediation of our experimental effects by neuroactive steroid levels and mRNA expression for neurosteroidogenic enzymes. The primary outcomes will be (10) levels of allopregnanolone as measured using GC-MS; average ICC of .29 in former K99 mentor's prior trials with 4 measures across the cycle in naturally cycling women), (11) gene expression for 5a-RI (no ICC estimate available for repeated administration; we assume a moderate ICC between .4-.6)., and (12) gene expression for 3a-HSDII.

ANALYTIC STEPS

Specification of Steps for Analytic Plan:

For each outcome, we will use model fit indices to select the best-fitting hierarchical model before proceeding with analyses. Based on our prior study (K99MH109667) with an similar experimental design and similar data collection structure for daily surveys and lab visits, we expect that the data structure for primary analyses will be observations nested within participants (two-level regression model). In our prior models, inclusion of a third level of nesting (i.e., observations nested within condition nested within individuals) did not improve model fit and did not substantively alter hypothesis tests. Based on the prior study, we also expect that a combination of a random intercept for participant and an autoregressive (day-1) within-person error structure will be included based on model fit.

Testing Experimental Effects: Both of our two aims require that we first evaluate the impact of the experiment on each of the 3 primary suicide outcomes and 9 (RDoC, neurosteroid) mediators described above. Therefore, we will first examine effects of the within-person hormone stabilization experiment on repeated measures outcomes across the menstrual cycle.

- a. For daily outcomes, we will utilize multilevel models (with 52 days—26 per condition-nested within each individual; two-level models) to predict each repeated measures outcome from covariates (daily pain, illness, PRN medication use) and the interaction between (1) experimental condition (a dichotomous variable coded as 0 for natural hormone withdrawal condition and 1 for hormone stabilization condition) and (2) condition phase, a categorical (contrast) variable coded as follows: *midluteal baseline phase*, coded as days +1 to +7 after the positive ovulation test, *perimenstrual experimental phase*, coded as days +11 to +17 after the positive ovulation test, and the *medication withdrawal phase*, coded as days +22 to +26 after positive ovulation test (see Figure 6 in grant for study design and timeline). Number of daily observations per person. For the primary contrast between the midluteal and perimenstrual experimental phases, there are 28 observations per person—14 per condition (7 midluteal, 7 perimenstrual). Based on our preliminary data from the K99 trial (identical experimental manipulation), we anticipate receiving an average of 24 observations per participant.
- b. For laboratory visit outcomes, we will again utilize multilevel models (with 6 labs per person—3 per condition—nested within individuals; two-level models). A two-level model will predict each repeated measures lab outcome from covariates (daily pain, illness, PRN medication use) and the interaction between (1) experimental condition (a dichotomous variable coded as 0 for natural hormone withdrawal condition and 1 for hormone stabilization condition) and (2) condition phase, a categorical (contrast) variable coded as follows: *midluteal baseline visit, perimenstrual experimental visit*, and the *medication withdrawal visit*. Number of lab observations per person. For the primary contrast between the midluteal and perimenstrual experimental phases, there are 4 observations per person—2 per condition. Based on our preliminary data from the K99 trial (identical experimental manipulation), we anticipate very minimal missing laboratory data (see grant for details) but have estimated that on average each completer participant will miss .25 visits.
- c. **Hypothesized Pattern of Effects for Daily and Lab outcomes**: A significant interaction between experimental condition and condition phase is hypothesized for all twelve specified outcomes such that, in the natural withdrawal condition we expect deleterious changes from the midluteal phase to the premenstrual and menstrual phases (due to corresponding hormone withdrawal), but in the hormone stabilization condition we expect no deleterious

1 R01 MH120843-01 (PI: [name])

changes (or less severe changes) from the midluteal to the premenstrual and menstrual phases (since hormone withdrawal is prevented).

2. Testing Associations Between Mediators and Suicide Outcomes: Each aim next requires that we evaluate the day-to-day or week-to-week associations between single mediators (listed above) and suicide outcome variables on the same day or visit. This will be carried out in similar multilevel models as above, predicting each of the three primary suicide outcomes from person-centered values for each of the 9 mediators (listed above).

3. Testing Interactive Effects of Hopelessness and Arousal on Suicide Outcomes: Interactions among hopelessness and arousal will be examined as predictors of suicide outcomes and as mediators of the experimental effect. In order to test this, we examine day-to-day interactive effects of daily person-centered hopelessness (noted above) and daily person-centered arousal indices (noted above) predicting same-daily suicide outcomes (noted above). We predict that higher-than-usual hopelessness on a given day will predict greater same-day risk on suicide outcomes, but only when arousal is *also* higher than usual for that individual.

4. Evaluating Mediation Where Appropriate. Finally, each aim indicates that **mediation** will be explored as appropriate. Only when analyses indicate significant effects of the experiment on both the suicide outcome and any mediator, as well as significant associations between the person-centered variable (or interaction variable) and the suicide outcome, we will utilize methods provided by **Bauer**, **Preacher**, **and Gil (2006)** to construct a confidence interval for the level 1 indirect effect of experimental condition (condition X phase) on the suicide outcome via the mediator.

1 R01 MH120843-01 (PI: [name]) POWER ANALYSIS.

With the funds allowed in this four-year grant, we are able to increase our proposed sample size slightly, from 80 to 85 completers, which would allow us to achieve 80% power to detect conventionally small-to-medium sized effects that, in our estimation, are clinically meaningful (i.e., $f^2 = .10$, which would mean that the interaction of condition and phase had uniquely accounted for 10% of the variance in the outcome in the perimenstrual window; Selya et al., 2012, "A Practical Guide to Calculating Cohen's f², a Measure of Local Effect Size"). We posit that if hormone withdrawal (vs. experimental stabilization) does not account for at least 10% of the variance in the outcome during this critical risky window of the menstrual cycle, then this line of research, which involves significant participant burden, is not worth pursuing further.

- Power in multi-level models has a unique consideration beyond sample size and alpha; it is dependent also on the intraclass correlation (ICC) and its implications for the independence of level-1 observations (i.e., the design effect). High ICCs indicate little variation of the outcome within a given person (i.e., stability of repeated observations within a given person), and suggest that the study's power depends more on the number of higher-level units. Low ICCs indicate high within-person variation within a given person and suggest that the study's power depends more on the number of lower-level units. As the ICC ranges from 0 to 1, the effective n will range from the number of lower-level units to the number of higher-level units. In general, the lower the ICC, the higher the power.
- Snijders and Bosker (1999; *Multilevel Analysis: An Introduction to Basic and Advanced Multilevel Modeling*) provide equations to determine the "Design Effect", which we have used to calculate the "effective lower-level N" based on our expected ICCs for each outcome and our expected number of raw observations with 85 completer participants (including 15% missing at daily level and an average of .25 missing visits per person). Once the design effect and effective N is calculated for a given outcome, one can calculate power to detect a given effect size (in our case, f² = .10) for a given number of these *effective* lower-level units (observations or visits)— see Table below for estimates for the current design. We considered a single fixed regression coefficient in a model with 3 predictors, one-tailed test, alpha=.004.
 

Variable	Measureme nt interval	ICC	Upper-Level Sample Size	Effective Lower- Level N based on ICC and Design Effect Equation	Power Achieved to detect f ² = .10
Suicidal Ideation	Daily	.64	85	130	.81
Suicidal Planning	Daily	.45	85	180	.93
Suicide Attempt	Daily	.12	85	542	.99
Beck Hopelessness Scale	Daily	.32	85	244	.98
Brief Agitation Measure	Daily	.26	85	292	.99
Accelerometer activity	Daily	.54	85	152	.88
Typing Speed Instability	Daily	.38	85	209	.96
HRV withdrawal in the lab	Labs	.50	85	163	.90
PEP shortening in the lab	Labs	.50	85	134	.83
Allopregnanolone in serum	Labs	.29	85	177	.93
PBMC gene expression for 3a- HSD	Labs	.50	85	134	.83
PBMC gene expression for 5a- reductase	Labs	.50	85	134	.83

1 R01 MH120843-01 (PI: [name])

Additional Requested Supplemental Table (2019-08-16)

Variable	Measurement interval	ICC in pilot data	P value	f-squared	Participants Needed to Achieve 80% Power in Proposed Model*
Suicidal Ideation	Daily	.64	.004	.10	83
Suicidal Planning	Daily	.45	.004	.10	57
Suicide Attempt	Daily	.12	.004	.10	21
Beck Hopelessness Scale	Daily	.32	.004	.10	45
Brief Agitation Measure	Daily	.26	.004	.10	37
Accelerometer activity	Daily	.54	.004	.10	71
Typing Speed Instability	Daily	.38	.004	.10	52
HRV withdrawal in the lab	Labs	.50	.004	.10	74
PEP shortening in the lab	Labs	.50	.004	.10	74
Allopregnanolone in serum	Labs	.29	.004	.10	53
PBMC gene expression for 3a-HSD	Labs	.50	.004	.10	74
PBMC gene expression for 5a-reductase	Labs	.50	.004	.10	74

[figure not shown]
*First, we calculated the number of observations required using a normal GLM framework (non-multilevel). Then, we calculated how many participants would be required to achieve that number of adjusted observations after penalizing for the anticipated design effect, which adjusts for the degree of non-independence in values (Snijders & Bosker, 1999) using the anticipated intraclass correlation (ICC) for each outcome. Anticipated ICCs are based on pilot data from prior studies.

1 R01 MH120843-01 (PI: [name])

• Plotting Power Across a Range of Participant-Level Sample Sizes. In addition, one can use the design effect equation to calculate expected power for a range of upper-level sample sizes (i.e., number of participants) adjusting for the most stringent design effect at that repeated measures interval (based on ICC=.64 for daily variables); see the figures below for power estimates across a range of possible participant-level sample sizes.

Effect of Number of Completer Participants on Power to Detect Effects of Intervention on Daily Outcomes in a Two-Level Regression Model (Days Nested within Participants)

[figure not shown]
(Inputs: Fixed Regression Model, 3 predictors, Bonferroni-corrected alpha=.004, Corrected for Design Effect Based on largest expected ICC of .64, and assuming 15% missingness per person)

Number of Completer Participants (Level-2 Units)

Effect of Number of Completer Participants on Power to Detect Effects of Intervention on Laboratory Outcomes in a Two-Level Regression Model (Visits Nested within Participants)

(Inputs: Fixed Regression Model, 3 predictors, Bonferroni-corrected alpha=.004, Corrected for "Design Effect" Based on largest expected ICC for lab visits .50, and assuming an average of .25 missing visits per person)

Number of Completer Participants (Level-2 Units)

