We define **hyperarousal** (RDoC Arousal and Regulatory Systems) as (1) self-reported agitation and overwhelm, (2) psychomotor agitation (smartphone accelerometer instability/movement^{13,14}), (3) behavioral reactivity to external stimuli (smartphone typing speed instability^{13,14}, attentional bias toward angry/fearful faces on task¹⁵), and (4) physiological hyperarousal (reduced resting parasympathetic autonomic function¹⁶, increased sympathetic and decreased parasympathetic autonomic function during an emotionally arousing task).

[figure not shown]
We define **hopelessness** as a state of despair *arising due to repeated experiences of loss or sustained threat* (RDoC Negative Valence Systems). It will be measured primarily as self-reported hopelessness using the Beck Hopelessness Scale (BHS)¹⁷, and we will measure lifetime and daily exposure to loss and threat^{18,19}.

We define **proximal suicide risk** as the presence and severity of self-injurious thoughts and behaviors as assessed dimensionally using the Adult SI Questionnaire (ASIQ)²⁰ and categorically using the Self-Injurious Thoughts and Behaviors Interview -Revised (SITBI-R). These instruments assess for passive and active SI; suicide plans; aborted, interrupted, and actual suicide attempts; and suicide death. Although non-suicidal self-injury (NSSI) is a distinct but related phenomenon, we also consider NSSI as an index of proximal risk given its predictive validity for suicide attempt²¹.

[figure not shown]
Premise for Aim 1a

Perimenstrual Hormone Withdrawal Causes Proximal Suicide Risk

In the first prospective study¹² of daily suicide risk in females with SI (K99MH109667), the PI found that proximal suicide risk peaks perimenstrually, during periods of natural hormone (E2+P4) withdrawal (Fig. 3). 38 females with past-month SI completed daily ratings on the ASIQ²⁰ across a baseline menstrual cycle. ASIQ scores peaked during the perimenstrual weeks relative to late follicular week, $\gamma=-.88$, $p<.001$ and early luteal week, $\gamma=-.56$, $p<.001$. We also observed greater odds of endorsing suicidal planning items on perimenstrual vs. non-perimenstrual days (OR=4.29, $p<.001$). 28 of 30 participants reported the highest mean SI perimenstrually. *These data support the premise that suicide risk peaks perimenstrually.*

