If a participant must be referred for emergency treatment (via emergency services/911 safety check, or walking the patient to the emergency room) at any point in the study, the blind will be broken for the participant and their study participation will be discontinued. If it is revealed that the participant was currently in the placebo condition, they will simply be referred to their mental health provider (or, as necessary, to the emergency department) for treatment. However, if it is revealed that the participant was currently in an active hormone stabilization condition, the supervising physician ([name]) will oversee a gradual tapering of the hormonal intervention and the patient will be referred to their mental health provider (or, as necessary, the emergency department) for treatment.

Protocol for Discontinuation and Referral. The protocol for discontinuation and referral is as follows. First, if the patient needs immediate inpatient evaluation or care, we will follow the protocol outlined in the UWRAP (see Appendix) to facilitate referral to emergency department (either via coordination with the emergency contact, by involving emergency services to perform a safety check at the participant's home, or by recruiting the help of UIC security to escort the patient from the outpatient psychiatry offices to the UIC emergency department. While the patient's immediate need for care is being attended to, the study staff will contact the investigational drug pharmacy and the blind will be broken for the study staff, the PI, and the participant. The participant will be notified that their study participation is discontinued and provided with instructions for either tapering medication (if active medication was being taken) or to follow up as needed with outpatient providers. If it is revealed that the participant was currently in an active hormone stabilization condition, [name] will oversee (or communicate with the participant's physician to recommend) a gradual tapering of the hormonal intervention.

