- ***Serious adverse event or serious suspected adverse reaction***. An AE or suspected adverse reaction is considered "serious" if, in the view of either the investigator or sponsor, it results in any of the following outcomes: death, a life-threatening adverse event, inpatient hospitalization or prolongation of existing hospitalization, or a persistent or significant incapacity. Important medical events that may not result in death, be life-threatening, or require hospitalization may be considered serious when, based upon appropriate

medical judgment, they may jeopardize the patient or subject and may require medical intervention to prevent one of the outcomes listed in this definition.

- *Notable examples of serious adverse events in the present study include development of a venous thromboembolism or suicide attempt.

AE STUDY-RELATEDNESS

For all AEs, [name] will urgently collaborate with [name] to determine the AE's causality based on temporal relationship and clinical judgment. The degree of certainty about causality will be graded using the categories below.

Definitely Related – There is clear evidence to suggest a causal relationship, and other possible contributing factors can be ruled out. The clinical event occurs in a plausible time relationship to drug administration and cannot be explained by concurrent disease or other drugs or chemicals. The response to withdrawal of the drug (dechallenge) should be clinically plausible. The event must be pharmacologically or phenomenologically definitive, with use of a satisfactory rechallenge procedure if necessary.

Probably Related – There is evidence to suggest a causal relationship, and the influence of other factors is unlikely. The clinical event occurs within a reasonable time after administration of the drug, is unlikely to be attributed to concurrent disease or other drugs or chemicals, and follows a clinically reasonable response on withdrawal (dechallenge). Rechallenge information is not required to fulfill this definition.

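### The attempt outcome (SAP outcome 3) is scored only from the daily phone screen, which is not scheduled on most baseline days, and no step adds attempts held in other trial records

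*SAP*

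**What the plan says.** The SAP (Outcome Specification, Suicide Outcome Variables) lists daily suicide attempt as the third of three primary suicide outcomes and specifies it as "dichotomous; aborted, interrupted, or full) on the daily C-SSRS phone risk screen". It expects a rare event: "1.2% of days were positive for suicide attempt in the K99 trial; ICC=.12 in K99 trial". No other source is named. Neither document gives a look-back period for the call, a rule for a missed call, or a step that adds attempts found by other means.

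For the primary contrast the SAP (Analytic Steps, item a) says "there are 28 observations per person—14 per condition (7 midluteal, 7 perimenstrual", and then "we anticipate receiving an average of 24 observations per participant". The Power Analysis handles missed days only as a smaller number of observations, "including 15% missing at daily level and an average of .25 missing visits per person".

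The Protocol sets the calendar in section 6.0. Medication starts at a visit seven days after the positive ovulation test and lasts two weeks. Safety calls take place on medication days and the four days that follow. Section 7.0 describes the call as a UWRAP screen of ideation, planning and intent.

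The Protocol also keeps other records of attempts:
- Section 6.0 (Self-Reports) gives a since-last-visit C-SSRS interview at every laboratory visit (days +7, +10, +14, +18, +22), coded with the C-CASA.
- Section 9.0 says "Notable examples of serious adverse events in the present study include development of a venous thromboembolism or suicide attempt".
- Section 9.0 also has the DSMB review data from discontinued participants.

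If a participant is referred for emergency treatment, section 7.0 says "the blind will be broken for the participant and their study participation will be discontinued".

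**The concern.** Followed as written, the SAP leaves unscored some attempts that the trial has itself recorded. There are three routes.

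1. **No call scheduled.** The baseline phase is days +1 to +7, but calls begin on day +7. The condition-by-phase contrast for this outcome would then rest on about one baseline day per condition.
2. **Call missed.** A missed day is simply absent, even when the next laboratory interview identifies an attempt on it.
3. **Call pre-empted.** An attempt that puts the participant in hospital before the call, and so ends participation, has no call that day or later. In this route the event causes its own missing value.

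The instrument is also in doubt. The SAP calls it the C-SSRS. The Protocol describes the UWRAP and does not list attempts among what the daily call covers.

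At stake is which events are counted in a rare, safety-critical primary outcome, and whether that count agrees with the trial's own serious adverse event listing.

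**Working it through.** **Step 1. Reproduce the SAP's power row for suicide attempt.** Inputs from the SAP Power Analysis: 85 completers, 24 observed days each, ICC .12, f² = .10, one-sided alpha .004, 3 predictors.

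Effective N = N·m / [1 + (m − 1)·ICC] = 85 × 24 / (1 + 23 × .12) = 2,040 / 3.76 = 542.6. The SAP gives 542.

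Power for one coefficient, from the noncentral t with noncentrality √(.10 × 542.6) = 7.37 and 542.6 − 4 = 538.6 degrees of freedom, is above .999. The SAP gives .99. The row reproduces.

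**Step 2. Lay the call calendar over the phases.** Two weeks of medication from day +7 are days +7 to +20 (my reading of the calendar). Four further days take calls to day +24.

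| Phase (SAP coding) | Days | Days with a scheduled call |
|---|---|---|
| Midluteal baseline | +1 to +7 | 1 of 7 |
| Perimenstrual | +11 to +17 | 7 of 7 |
| Medication withdrawal | +22 to +26 | 3 of 5 |

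In the primary contrast, calls cover 2 × (1 + 7) = 16 of 28 days per person. The SAP's expected 24 observations therefore cannot all come from the call.

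**Step 3. Expected attempt-days at the SAP's own rate.**
- All planned days: 85 × 28 × .012 = 28.6.
- Expected observed days: 85 × 24 × .012 = 24.5.
- Unobserved at the same rate: 85 × 4 × .012 = 4.1, which is 4.1 / 28.6 = 14%.

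If the rate on missed days is k times the rate on observed days (k is assumed; the documents give no value):

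| k | Unobserved attempt-days | Share of all attempt-days |
|---|---|---|
| 1 | 4.1 | 14% |
| 2 | 8.2 | 25% |
| 3 | 12.2 | 33% |
| 5 | 20.4 | 45% |

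These rows use the SAP's 24 of 28 days at face value. The call calendar alone leaves 12 of 28 days per person without a call. At a uniform 1.2% that would be 85 × 12 × .012 = 12.2 attempt-days. A uniform rate is doubtful here, because the plan expects lower risk at baseline, so this is a reference figure and not an estimate.

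**Step 4. Effect on the SAP's stated power.**
- Every contrast day filled: 85 × 28 / (1 + 27 × .12) = 2,380 / 4.24 = 561.3, power above .999.
- Called days only: 85 × 16 / (1 + 15 × .12) = 1,360 / 2.80 = 485.7, power above .999.

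By the SAP's own method, power barely moves. The problem is which events are counted.

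**Step 5. The pre-empted call.** These figures concern completers. Participants discontinued after an emergency lie outside the 85, and neither document gives a rate for them, so this route cannot be sized.

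**The case against.** The strongest reply is that only a linking sentence is missing. The SAP does not forbid adding events from other records. The laboratory interview is meant to capture discrete behaviours, it is coded into suicide outcomes, and visits are at most four days apart across the perimenstrual window. Section 8.0 refers missing data to the principal investigator for resolution. An attempt disclosed on a call that then leads to referral would be scored, and a next-day call might pick up an attempt from the day before. The 15% is a general rate for daily measures and not a call completion rate; calls are also paid for separately. All of this stands, and it limits the point. It does not remove it: no analysis step carries those records into outcome 3, and no look-back for the call is stated.

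Three stronger readings are tempting, and the documents do not support them.

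- **That the losses must shrink the condition difference.** Random misses remove a day from both the numerator and the denominator of the rate. Equal proportional loss in both conditions leaves the ratio unchanged. Loss that depends on the event could bias the contrast, but the documents do not fix its direction or size.
- **That power falls sharply.** One could treat the prior trial's 2 versus 0 participants with aborted attempts (Protocol 2.0) as a paired person-level comparison and delete 15% of them. The plan runs no such test, that count covers aborted attempts only, and losing 15% of days is not losing 15% of affected people.
- **That attempts leading to hospital are a known, sizeable loss.** Protocol 4.1 reports that nobody in the prior trial was hospitalised for imminent risk or attempted suicide.

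Suicide death also needs care. Protocol 2.0 says that the instruments cover "aborted, interrupted, and actual suicide attempts; and suicide death", but outcome 3 does not include death, so adding it would change the outcome.

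**Conclusion.** The point holds as a poor stated rule with a ready replacement. Outcome 3 has one source. On the Protocol's calendar that source is absent on about six of seven baseline days per condition, and no rule covers a missed or pre-empted call. The two documents also disagree on the instrument used in the call.

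The total loss cannot be computed from the documents. On the SAP's figures, about 4 of 28.6 expected attempt-days in the primary contrast would be unobserved if misses are unrelated to attempts; the share is 25% to 45% if attempts are 2 to 5 times as frequent on missed days (assumed). These counts depend on the 1.2% rate, which is uncertain. Over 30 people it implies 30 × 28 × .012 = 10.1 to 30 × 52 × .012 = 18.7 positive days, depending on which days were counted, while the Protocol reports two participants with aborted attempts. The SAP's stated power is essentially unchanged, so the case for change rests on complete and consistent counting.

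**What to change.** Before unblinding, amend the SAP as follows.

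1. Define outcome 3 as an aborted, interrupted or actual attempt dated to its day from any study record: daily call, laboratory C-SSRS with C-CASA coding, serious adverse event report, or discontinuation record.
2. Use the laboratory interview to fill uncalled and missed-call days through day +22. Set its look-back at the day +7 visit to reach day +1, and record a date for each event.
3. Score an attempt that ends participation on the date it occurred.
4. Have events classified and dated from records with condition removed, by a team member not unblinded for that participant. Discontinuation unblinds study staff and the principal investigator, so this person must be kept apart.
5. Report any suicide death alongside outcome 3, not silently within it.
6. Reconcile the SAP's C-SSRS call with the Protocol's UWRAP call, and state the call's look-back and whether it asks about attempts.

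The cost is SAP wording, a specified interview look-back, one reconciliation step across the call, interview and safety records, and one coder kept blind. The downside is that recovered events have less exact dates. Days +23 to +26 have no later laboratory visit in that condition to fill them, and on the calendar above +25 and +26 have no call either.
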